1.1.5 Nanostring platform for gene expression analysis of formalin-fixed paraffin embedded tumor

Gene expressing profiling performed by the nanostring technology, which utilizes formalin-fixed paraffin embedded (FFPE) tissue using the nCounter® appears highly promising (82). This technology provides robust data from FFPE tissue using the nCounter® GX Kit and offers high levels of precision and sensitivity (>1 copy per cell) without the need for amplification of ≥ 100 ng of RNA. Nanostring is a multiplexed (up to 800 genes per reaction) platform, which utilizes digital counting and excellent quantitative reproducibility by employing two ~50 base probes per mRNA that hybridize in solution. Multiple successful applications utilizing the nCounter System to subtype tumors, formulate tumor prognostic signatures, or discover novel targets for therapy have been reported in other malignancies (83-86). Notably, the 50-gene PAM50 signature (Prosigna™) derived from nanostring was approved by the US FDA in 2013 to assess the risk of distant recurrence at 10 years in postmenopausal women with hormone receptor-positive breast cancer. Indeed, the PAM50 gene score, which is enriched for proliferation-associated genes appeared more robust than the Oncotype DX® recurrence score in predicting recurrence (85).

1.1.6 Activity of EGFR inhibitors in PSCC

A potential role may exist for EGFR inhibitors in PSCC as shown in small retrospective studies of EGFR targeting monoclonal antibodies (87-89). In one retrospective study, all 13

patients with advanced PC expressed EGFR with 77% exhibiting 3+ levels of expression and received EGFR-targeted therapies, including erlotinib (n = 1), cetuximab (n = 3) or cetuximab, combined with platinum-based regimens (n = 9). The patients showed a median TTP of 3.2 months and a median OS of 9.8 months. Four (31%) patients survived between 13 and 48+ months, comparing favourably with historical survival when utilizing conventional chemotherapy. Anecdotal responses have been reported with panitumumab or combination docetaxel–cetuximab after cisplatin-based chemotherapy. Hence, a rationale exists to investigate the activity of EGFR inhibitors in general, and Gilotrif in particular, which is a pan-HER family inhibiting TKI.

1.2 DRUG PROFILE OF GIOTRIF

Gilotrif (BIBW2992) is a small molecule, selective and irreversible erbB family blocker. In preclinical models it effectively inhibits EGFR, HER2 and HER4 phosphorylation resulting in tumour growth inhibition and regression of established subcutaneous tumours derived from four human cell-lines known to co-express ErbB receptors.

For the latest information on the drug profile of Gilotrif, please refer to the current Investigator's Brochure (IB) (U03-3218). All references in this protocol concerning Gilotrif refer to the free base compound Gilotrif BI which is used as the oral formulation.

Gilotrif is moderately fast absorbed after oral administration. Maximum plasma concentrations of Gilotrif were achieved mainly at 2 to 5 hours after oral drug administration. Gilotrif maximum plasma concentrations and area under the curve increased slightly over-proportional with increasing doses in the therapeutic range of 20-50mg. Moderate to high inter- and intra-individual differences in plasma concentration were seen. Gilotrif is highly distributed out of the blood and has a moderate to high clearance. The overall gMean terminal half-life at steady state was 37.2 hours in cancer patients. Steady state was reached no later than 8 days after the first administration. The major route of elimination of Gilotrif was via faeces. After food intake, a decreased systemic exposure was observed compared to administration under fasted conditions. Therefore, Gilotrif should be taken without food (i.e. 1 hour before or 2 hours after food). The PK characteristics in Caucasian cancer patients were comparable to those observed in Japanese cancer patients.

Gilotrif is bound covalently to proteins to a variable extent and covalent protein adducts were the major circulating metabolites in the plasma. Gilotrif did not show relevant inhibition or induction of cytochrome P450 isoenzymes, and it appears unlikely that drug-drug interactions based on this mechanism will occur.

Gilotrif is a substrate of the P-gp transporter. Concomitant administration of the potent P-gp inhibitor ritonavir did not relevantly change the exposure to 40 mg Gilotrif when taken simultaneously with or 6 h after Gilotrif but increased the bioavailability of Gilotrif (single dose of 20 mg) by 48% and 39% for AUC_{0-∞} and Cmax when given 1 h before Gilotrif, respectively. Pretreatment with the potent P-gp inducer rifampicin decreased the plasma exposure of 40 mg Gilotrif by 34 % Gilotrif (AUC_{0-∞}) and 22 % (Cmax), respectively. Caution should be exercised when combining Gilotrif with potent P-gp modulators. In pre-clinical studies Gilotrif is not irritant to intact skin but an ocular irritant. Gilotrif is mutagenic in a single bacteria strain, but did not show genotoxic potential in vivo when tested up to overt toxic/lethal doses. Studies on embryo-foetal development in rats and rabbits up to life-threatening doses have revealed no indication of teratogenicity.

Two phase I open label dose-escalation studies determined the MTD with continuous dosing of Gilotrif in patients with advanced solid tumours at 40mg and 50mg daily, respectively (90, 91). Adverse events (AE) observed with Gilotrif are consistent with those reported for other EGFR and dual EGFR/HER2 inhibitors. The most frequent investigator defined drug-related AEs were associated with gastrointestinal disorders (including diarrhoea, and stomatitis), skin and subcutaneous tissue disorders (rash, dry skin, pruritus, acneiform rash, acne), nail effects, epistaxis, fatigue and decreased appetite. Early and proactive management of diarrhoea, mucositis/stomatitis and skin rash together with treatment interruptions and dose reductions is recommended in line with recent guidelines in the management of common toxicities of EGFR and EGFR/HER2 TKIs and monoclonal antibodies (92-96).

2. RATIONALE, OBJECTIVES, AND BENEFIT - RISK ASSESSMENT

2.1 Rationale for performing the trial evaluating Gilotrif as salvage therapy for advanced PSCC

Gilotrif is a highly promising irreversible pan-EGFR inhibitor, which was recently approved for non-small cell lung cancer with EGFR mutations (97). Median PFS was 11.1 months for Gilotrif and 6.9 months for chemotherapy with cisplatin plus pemetrexed in a phase III trial (hazard ratio [HR], 0.58; 95% CI, 0.43 to 0.78; $P = .001$). Median PFS among those with exon 19 deletions and L858R EGFR mutations ($n = 308$) was 13.6 months for Gilotrif and 6.9 months for chemotherapy (HR, 0.47; 95% CI, 0.34 to 0.65; $P = .001$). The most common treatment-related adverse events were diarrhea, rash/acne, and stomatitis for Gilotrif and nausea, fatigue, and decreased appetite for chemotherapy. Given the tumor tissue studies providing robust supportive evidence for the expression of the EGFR family of proteins, a strong rationale may be made for investigating the role of Gilotrif as salvage therapy for advanced PSCC. Indeed, another phase II trial is evaluating dacotinib, another pan-Her inhibitor as salvage therapy for PSCC (NCT01728233). Moreover, PSCC is an orphan malignancy and a strong rationale can be made for the approval of agents by regulatory agencies based on robust activity in phase II trials.

2.2 Study objectives

2.2.1 Primary objective

Progression-free survival (PFS) at 6 months of patients with advanced PSCC receiving Gilotrif following ≥ 1 prior systemic therapy regimen

2.2.2 Secondary objectives

- Response Rate (RECIST 1.1)
- Overall Survival
- Toxicities

2.2.3 Exploratory objectives

- Tumor tissue molecular studies: HPV status (PCR), gene expression (nanosting) and IHC (EGFR, Her2, Her3, Her4)
- Central pathology review and histologic subtype

2.3 Benefit-Risk Assessment

Gilotrif offers the prospect of prolonged PFS in a proportion of patients with progressive disease following systemic therapy for PSCC. Potentially some patients will exhibit a response accompanied by improvement in symptoms and quality of life. The major adverse

events are expected to be diarrhoea, rash/acne, and stomatitis, which are manageable and not life threatening. Given that patients with progressive PSCC following prior systemic therapy have no curative options and dismal outcomes with currently employed agents, the potential benefits with Gilotrif clearly outweigh the risks. Moreover, there are no agents approved by regulatory agencies for this disease.

3. DESCRIPTION OF DESIGN AND STUDY POPULATION

3.1 Overall study design and plan

[figure not shown]
This is a non-randomized 2-center phase II trial (overall N=29, evaluable N= 27) to evaluate Gilotrif 40 mg po qd for patients with locally advanced unresectable or metastatic progressive PSCC following prior chemotherapy. UAB is the coordinating institution and the other participating institution is the University of Southern California (USC). Patients will undergo clinical examination every 4 weeks and radiographic work-up at baseline and then every 8 weeks. Patients will continue therapy until progression or intolerable toxicities. Patients removed from therapy for reasons other than progression will be followed to identify progression or until initiation of other therapy. Twenty archival formalin-fixed paraffin embedded (FFPE) tissue slides per patient will be acquired for future analyses including histologic sub-type, IHC for EGFR, Her2, Her3, Her4, gene expression by nanostring for a panel of kinase and cancer associated genes and Human Papilloma Virus status by PCR (polymerase chain reaction) for HPV-DNA.

The eligible population of patients includes men with pathologically proven locally advanced or metastatic (lymph node or distant metastasis i.e. N+ or M1) PSCC which has received ≥ 1 systemic chemotherapy regimens within last 6 months with ECOG PS 0-2 & optimal organ function (Hb>8.5, ANC>1500/mm³, Platelet count>100K, Total bilirubin <1.5 of ULN, creatinine clearance >45ml/min, ALT and AST<2.5X ULN, for patients with liver involvement ALT and ALT<5X ULN). The disease should be measurable by RECIST 1.1 criteria. Gilotrif will be administered orally 40mg daily continuously. Continuous administration of 4 weeks is considered one cycle. Therapy will continue until progression (by RECIST 1.1) or severe toxicities. Patients removed from the trial for toxicities or other reasons will continue to be followed until progression or starting a new agent. Complete Blood Count (CBC) & Comprehensive metabolic panel (CMP) evaluations will be done performed on day 1 every 4 weeks. CT chest, abdomen and pelvis will be performed every 2 cycles (8 weeks). A bone scan will be performed only if bone pain or high alkaline phosphatase are observed. An evaluable patient is defined as any patient who qualifies for the trial and receives at least one dose of study drug.

Progression of disease will be defined clinically as the first occurrence of any of the following:

- 1) Progression in measurable disease as defined by RECIST criteria
- 2) Death

Trial schema

3.2 Discussion of study design

Given that there are no approved agents and PSCC is an orphan disease, demonstration of activity and benefit of a salvage systemic agent in a nonrandomized phase II trial is reasonable. Currently used agents, e.g. taxanes, yield marginal activity and exhibit median PFS and OS of only ~3 months and ~6 months, respectively (Table 1). Given the lack of validated predictive biomarkers for efficacy and the universal presence of EGFR in PSCC, all patients will be enrolled without biomarkers to select a subgroup. Those progressing within 6 months of prior therapy will be enrolled with the goal of detecting PFS at 6 months (PFS6) in ≥20% of patients, while PFS6 in <5% will be considered to be of poor interest. The attainment of PFS at 6 months by ≥20% of patients is considered of significant interest, since this was not achieved in the second-line trial that evaluated paclitaxel (78). Selecting patients within 6 months of prior therapy will enrich for patients unlikely to attain PFS6 without active therapy.

Trial schedule

	-30 days	-14 days	Day 1 of every cycle (28 days)	Every 2 cycles	28 (\pm 3 days) post last treatment
REQUIRED ASSESSMENTS					
History	X		X		X
Height	X				
Physical examination		X	X		X
BP, weight		X	X		X
Smoking history	X				
ECOG performance status		X	X		X
CBC with differential		X	X		X
Chemistries (CMP)		X	X		X
Hepatitis panel (B, C)	X				
Adverse event and concomitant medication assessment	X		X		X
DISEASE ASSESSMENT					
CT chest, abdomen, pelvis	X			X	X
Bone Scan (if bone pain or high alkaline phosphatase)	X			X	
TREATMENT					
Gilotrif PO QD			X (1-28 days)		
CORRELATIVE STUDIES					
Collect 20 FFPE slides (15 sections of 10 μ M thickness, 5 sections of 5 μ M thickness) from archival biopsy for correlative studies (central pathology review, IHC, nanostring gene expression, HPV DNA)	X				
FOLLOW-UP					
Disease progression and survival					X

3.3 Selection of study populationGeneral Guidelines

Eligible patients will be entered on study centrally at the Kirklin Clinic, UAB Hospitals, and USC (research nurse to be designated by [name] Director of Oncology Clinical Trials, CSU, UAB). All sites should call the Study Monitor at UAB to verify agent availability. Following registration, patients should begin protocol treatment within 72 hours. Issues that would cause treatment delays should be discussed with the Principal Investigator. If a patient does not receive protocol therapy following registration, the patient's registration on the study may be cancelled. The Study Monitor should be notified of cancellations as soon as possible.

Registration Process

The Clinical Trials Network Monitoring Office (CTNMO) of the UAB Comprehensive Cancer Center (CCC) coordinates investigator-initiated clinical trials under Good Clinical Practice conditions at participating sites to achieve timely study subject enrolment. Once a study subject has been screened and deemed eligible for study entry by the participating site, a study-specific study subject eligibility checklist, a copy of the dated and signed consent form, and corresponding source documentation are faxed to the participating site study coordinator for eligibility verification. Subsequently, a study-specific number is assigned to the study subject and sent to the participating site. Finally, a Patient Registration Form is completed and faxed by the CTNMO site to the participating study coordinator. Queries regarding data accuracy are forwarded from the CTNMO to the participating site coordinator for clarification or correction. Once the participating site addresses queries, any corrected data forms or copies of corrected source documentation are faxed to the CTNMO.

3.3.1 Main diagnosis for study entry

Patients who have been detected with histology confirmed Penile Squamous Cell Carcinoma (PSCC) and who have documented failure after at least one prior chemotherapy

3.3.2 Inclusion criteria

1. Each patient will meet all of the following criteria to be enrolled in the study: Histologically or cytologically confirmed PSCC.
2. Patients with metastatic (lymph node or distant metastasis, i.e. N+ or M1) or locally advanced unresectable PSCC.
3. Progressive disease after ≥ 1 prior chemotherapy regimens.
4. Measurable disease by RECIST 1.1 criteria.
5. Prior regimen within 6 months
6. ECOG performance status 0-2 (*Appendix 10.3*).
7. Adequate organ function, defined as all of the following:
 - Absolute neutrophil count (ANC) $> 1500 / \text{mm}^3$. Platelet count $> 100,000 / \text{mm}^3$.
 - Estimated creatinine clearance $\geq 45 \text{ml} / \text{min}$. Refer to *Appendix 10.2*.
 - Total Bilirubin < 1.5 times upper limit of institutional normal; Aspartate amino transferase (AST) or alanine amino transferase (ALT) < 2.5 times the upper limit of institutional normal (ULN).
 - Hemoglobin $\geq 8.5 \text{ g/dl}$.
8. Resolution of all acute toxic effects of prior chemotherapy or surgical procedures to NCI CTCAE version 4.03 grade < 1 , in the opinion of the Treating Physician (*Appendix 10.7*).
9. Ability to understand and willingness to sign a written informed consent that is consistent with ICH-GCP guidelines. Age ≥ 18 years or age of majority at the participating site, whichever is greater.

10. Availability of 20 archival formalin-fixed paraffin embedded (FFPE) tumor tissue slides (15 of 10 µM thick sections, and 5 of 5 µM thick sections)

3.3.3 **Exclusion criteria**

Patients meeting any of the following exclusion criteria within 4 weeks (unless otherwise stated) of being enrolled are not to be enrolled in the study.

1. Patients will have recovered from toxicities from prior systemic anticancer treatment or local therapies.
2. Prior EGFR inhibitors.
3. Major surgery within 4 weeks or minor surgery within 2 weeks before registration or scheduled for surgery during the projected course of the study. Wounds will be completely healed prior to study entry and patients recovered from all toxicities from surgery. Placement of vascular access device is not considered major or minor surgery in this regard.
4. Prior radiation therapy is allowed as long as the irradiated area was not the sole source of measurable disease and radiotherapy was completed with recovery from toxicity, at least 3 weeks prior to enrollment. If the irradiated area is the only site of disease, there will be progressive disease.
5. History or presence of clinically relevant cardiovascular abnormalities such as uncontrolled hypertension, congestive heart failure NYHA classification of 3 (Refer to Appendix 10.6), unstable angina or poorly controlled arrhythmia as determined by the investigator. Myocardial infarction within 6 months prior to registration.
6. Any history of or concomitant condition that, in the opinion of the Investigator, would compromise the patient's ability to comply with the study or interfere with the evaluation of the efficacy and safety of the test drug
7. Previous or concomitant malignancies at other sites, except effectively treated non-melanoma skin cancers, ductal carcinoma in situ or effectively treated malignancy that has been in remission for more than 3 years and is considered to be cured.
8. Requiring treatment with any of the prohibited concomitant medications listed in Section 4.2.3 that cannot be stopped for the duration of trial participation
9. Known pre-existing interstitial lung disease
10. Any history or presence of poorly controlled gastrointestinal disorders that could affect the absorption of the study drug (e.g. Crohn's disease, ulcerative colitis, chronic diarrhea, malabsorption)
11. Active hepatitis B infection (defined as presence of Hep BsAg and/ or Hep B DNA), active hepatitis C infection (defined as presence of Hep C RNA) and/or known HIV carrier.
12. Meningeal carcinomatosis
13. Patients with active brain or subdural metastases are not eligible, unless they have completed local (radiation) therapy and have discontinued the use of corticosteroids or have been on stable dose of corticosteroids for at least 4 weeks before starting study treatment. Any symptoms attributed to brain metastases will be stable for at least 4 weeks before starting study treatment.
14. Any active or uncontrolled infection.

3.3.4 Removal of patients from therapy or assessments

Patients will be removed from study when any of the criteria listed below applies. The reason for study removal and the date the patient was removed will be documented in the Case Report Form.

1. Progression of disease as defined by measurable disease using RECIST 1.1
2. Death
3. Intercurrent illness that prevents further administration of treatment
4. Unacceptable adverse event(s)
5. Patient decides to withdraw from the study
6. General or specific changes in the patient's condition render the patient unacceptable for further treatment in the judgment of the investigator.

3.3.5 Premature discontinuation of the study as a whole

The study will be discontinued in event of

1. Deviation in conduct of protocol
2. No accrual in first year
3. >1 death attributable to toxicity from study drug
4. If no patient, out of 13 accrued patients achieves PFS6 at the end of stage 1, this study will be stopped.

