Statistical methods: PFS6 is chosen as the primary end-point. Given the poor prognosis of this patient population and data from other studies of salvage therapy, a PFS6 of $\geq 20\%$ is considered to be important for this regimen, while a PFS6 $< 5\%$ will be considered to be of poor interest. A total of 27 evaluable subjects will be enrolled, 13 during stage 1 and 14 during stage 2 of a two-stage minimax design phase II study. The alpha level of the design is 0.05 and the power is 0.8. If no patients are free from progression at 6 months during the first stage then the trial ends with the conclusion that this drug is not worth further study. Otherwise it proceeds to the second stage. If less than 4 of the 27 patients are progression free at 6 months, it will be concluded that the drug is not worth further study. Given that 5-10% of enrolled patients are inevaluable, up to 29 patients may be enrolled.		
Study duration	This study will be conducted over 12-18 months. Accrual period will be 6-12 months.	

FLOW CHART

	-30 days	-14 days	Day 1 of every cycle (28 days)	Every 2 cycles	28 (± 3 days) post last treatment
REQUIRED ASSESSMENTS					
History	X		X		X
Height	X				
Physical examination		X	X		X
BP, weight		X	X		X
Smoking history	X				
ECOG performance status		X	X		X
CBC with differential		X	X		X
Chemistries (CMP)		X	X		X
Hepatitis panel (B, C)	X				
Adverse event and concomitant medication assessment	X		X		X
DISEASE ASSESSMENT					
CT chest, abdomen, pelvis	X			X	X
Bone Scan (if bone pain or high alkaline phosphatase)	X			X	
TREATMENT					
Gilotrif PO QD			X (1-28 days)		

CORRELATIVE STUDIES	
Collect 20 FFPE slides (15 sections of 10uM thickness, 5 sections of 5uM thickness) from archival biopsy for correlative studies (central pathology review, IHC, nanostring gene expression, HPV DNA)	X
FOLLOW-UP	
Disease progression and survival	X

TABLE OF CONTENTS

TITLE PAGE	1
CLINICAL STUDY PROTOCOL SYNOPSIS.....	6
FLOW CHART	11
TABLE OF CONTENTS	13
ABBREVIATIONS	16
1. INTRODUCTION	18
1.1 MEDICAL BACKGROUND	18
1.2 DRUG PROFILE	22
2. RATIONALE, OBJECTIVES, AND BENEFIT - RISK ASSESSMENT.....	23
2.1 Rationale for performing the study	23
2.2 Study objectives	23
2.2.1 Primary objective.....	23
2.2.2 Secondary objective.....	23
2.2.3 Benefit-Risk Assessment	23
3. DESCRIPTION OF DESIGN AND STUDY POPULATION	24
3.1 Overall study design and plan	24
3.2 Discussion of study design.....	25
3.3 Selection of study population	26
3.3.1 Main diagnosis for study entry	27

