7. STATISTICAL METHODS AND DETERMINATION OF SAMPLE SIZE

7.1 Statistical design-model

Given the poor prognosis of this patient population and data from other studies of salvage therapy, a PFS6 of $\geq 20\%$ is considered to be important for this regimen, while a PFS6 $< 5\%$ will be considered to be of poor interest. A two-stage minimax design will be used which will enroll a maximum of 27 subjects: 13 during stage 1 and 14 during stage 2. If no patients are free from progression at 6 months among 13 patients during the first stage, then the trial ends with the conclusion that this drug is not worth further study. Otherwise the trial proceeds to the second stage. Since some (5-10%) accrued patients may not be evaluable, up to 29 patients will be enrolled.

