7.2 Null and alternative hypotheses

The null hypothesis for this study is that PFS at 6 months will occur in less than 5% after treating with Gilotrif whereas the study alternative hypothesis is that PFS at 6 months will be observed in 20% or more of all patients, which will signify important activity of Gilotrif in this patient population.

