7.3.3 Interim analyses

At the end of Stage 1, when 13 patients have been recruited and PFS6 has been calculated for these subjects, an interim analysis will be conducted to determine futility of the study. If none of these subjects are progression free at 6 months, the study will be stopped early due to futility and we will conclude the drug is of poor interest. If one or more subjects are progression free, we will proceed to Stage 2.

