7.5 Determination of sample size

SAS version 9.3 was used to calculate power and determine sample size. The justification for the proposed sample size is based on applying an exact test for a binomial proportion to Simon's two-stage minimax design(103). A one-sided significance level of 5% was used. Under this design, we will have approximately 80% power (80.1%) to reject the null hypothesis that $PFS < 5\%$ in favour of $PFS6 \geq 20\%$.

A total of up to 29 patients will be enrolled including 27 evaluable patients for this trial. Accrual period will be ~12 months. Follow-up will be at least 6 months after the last patient starts therapy. Thus, the overall duration of the trial is expected to be ~18 months.

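### The stage 1 futility stop in section 3.3.5 counts 13 accrued patients, but the design counts 13 evaluable patients; the wording should be aligned, although the loss of power is small

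*Combined protocol and SAP*

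**What the plan says.** The stage 1 rule appears in four places, with different denominators.

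- **Synopsis, Statistical methods:** "A total of 27 evaluable subjects will be enrolled, 13 during stage 1 and 14 during stage 2". The stop for zero successes in the first stage follows, so its 13 are evaluable subjects.
- **Section 7.1:** "If no patients are free from progression at 6 months among 13 patients during the first stage", the trial ends. These 13 sit inside a maximum of 27. The same paragraph says 5-10% of accrued patients may not be evaluable and allows up to 29 enrolments for that reason. Accrued and evaluable are therefore different counts in this plan.
- **Section 3.3.5, item 4:** "If no patient, out of 13 accrued patients achieves PFS6 at the end of stage 1, this study will be stopped".
- **Section 7.3.3:** the interim takes place "when 13 patients have been recruited and PFS6 has been calculated for these subjects".

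Section 3.1 defines an evaluable patient as one who is eligible and has taken at least one dose. Section 3.3 (General Guidelines) asks for treatment to start within 72 hours of registration and allows the registration of an untreated patient to be cancelled.

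**The concern.** Section 3.3.5 lists the conditions that end the study. Taken at its word, item 4 fixes the group at 13 accrued patients, some of whom the plan expects to be ineligible or undosed. Such patients cannot supply a PFS6 success. The rule of zero successes would then act on 12 or fewer evaluable patients and be stricter than the design that was sized.

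This is the only efficacy futility look, and it turns on 0 against 1 success. If the denominator is not settled beforehand, someone must decide whether an ineligible or undosed patient belongs to the 13 when the result may already be visible. The error can only raise the chance of abandoning an active drug.

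**Working it through.** **Inputs.** Null PFS6 5% ("PFS at 6 months will occur in less than 5% after treating with Gilotrif", section 7.2); alternative 20% ("PFS at 6 months will be observed in 20% or more of all patients", section 7.2); "A one-sided significance level of 5% was used" (section 7.5); stages of 13 and 14 evaluable (synopsis); stop at 0 of 13 (sections 7.1 and 7.3.3); success at 4 or more of 27 (section 7.3.1); inevaluable rate d = 5-10% and cap of 29 (section 7.1).

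**Step 1: reproduce the plan's power.** Section 7.5 states: "Under this design, we will have approximately 80% power (80.1%) to reject the null hypothesis". Power = Σ over x ≥ 1 of P(X₁ = x | 13, 0.20) × P(X₂ ≥ 4 − x | 14, 0.20).

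- x = 1: 0.1787 × 0.5519 = 0.0986
- x = 2: 0.2680 × 0.8021 = 0.2150
- x = 3: 0.2457 × 0.9560 = 0.2349
- x ≥ 4: 0.2527 × 1 = 0.2527

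The sum is 0.801, or 0.8011 at full precision. The stated 80.1% is right. The same formula at 5% gives a type I error of 0.0416. An exhaustive search confirms that this is the minimax design for these inputs.

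**Step 2: how often the two counts differ.** P(at least one of 13 accrued is inevaluable) = 1 − (1 − d)¹³, which is 1 − 0.95¹³ = 49% at 5% and 1 − 0.90¹³ = 75% at 10%. Two or more have probability 1 − (1 − d)¹³ − 13d(1 − d)¹², about 14% and 38%.

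**Step 3: wrongful stop at true PFS6 of 20%.** With n evaluable patients it is 0.8ⁿ. Averaged over the number evaluable, it is (1 − 0.20(1 − d))¹³.

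- 13 evaluable: 0.8¹³ = 5.5%
- 12 evaluable: 0.8¹² = 6.9%
- 11 evaluable: 0.8¹¹ = 8.6%
- Average at d = 5%: 0.81¹³ = 6.5%
- Average at d = 10%: 0.82¹³ = 7.6%

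**Step 4: power if 27 evaluable are finally reached.** Repeat step 1 with a first stage of k and a second stage of 27 − k: k = 13 gives 80.1%, k = 12 gives 79.4%, and k = 11 gives 78.3%. Weighting by the binomial probability that k of 13 are evaluable gives 79.6% at d = 5% and 78.9% at d = 10%, a loss of 0.5 to 1.2 points. Type I error falls from 4.16% to 4.10-4.04%.

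**Step 5: separate the effect of the 29-patient cap.** At d = 10%, 27 evaluable need 27 / 0.90 = 30 enrolments, and 29 yield an expected 29 × 0.90 = 26.1. With the cap applied:

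| Inevaluable | Gate on 13 evaluable | Gate on 13 accrued |
|---|---|---|
| 5% | 79.5% | 79.0% |
| 10% | 77.3% | 76.3% |

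The gate wording accounts for about 0.5 to 1.0 point here. At 10%, most of the distance from 80.1% comes from the cap.

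**The case against.** The strongest reply is that the plan, read as a whole, already gates on evaluable patients. The synopsis says so, section 7.1 places the 13 within the 27 and not within the 29, and section 7.3.3 requires PFS6 to be known for the 13. Only section 3.3.5 says accrued, in one line of a list outside the statistical section. In addition, few patients can be accrued yet inevaluable: eligibility is verified before a study number is issued, and an untreated patient's registration may be cancelled. Applying the full 5-10% to the first 13 is therefore a literal, upper-end reading.

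Most of this stands, and it limits the point to a conflict in wording. It does not remove the conflict. Cancellation is optional and does not cover a dosed patient later found ineligible. Section 7.3.3 does not say that an inevaluable recruit is replaced. A calculated PFS6 is also not the same criterion as evaluable in section 3.1.

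A reader might infer more: that the trial fails its stated power, or that the interim will usually be run on 11 or 12 patients. The documents do not support either. Section 7.5 claims approximately 80%, and 79.6-78.9% is close to that. The interim would run short only under the literal reading of section 3.3.5, which the rest of the plan makes the less likely one.

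**Conclusion.** The point holds as an inconsistency in a binding stopping rule. Section 3.3.5 conflicts with the synopsis and with the distinction drawn in section 7.1, and section 7.3.3 only partly resolves it. The literal reading adds 1.0 to 2.1 percentage points to the chance of wrongly stopping a drug with true PFS6 of 20% and costs 0.5 to 1.2 points of power, always to the disadvantage of an active drug.

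These figures assume that inevaluability occurs in stage 1 at the plan's 5-10% rate, that it is independent of outcome, that an inevaluable patient cannot count as a success, and that 27 evaluable patients are finally reached. If cancelled registrations leave the count, the effect is smaller. The chosen two-stage design and its stated power are correct. The reason to act is that the rule should be unambiguous before stage 1 data are seen, not that the loss is large.

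**What to change.** In section 3.3.5, item 4, and in section 7.3.3, state the gate on the first 13 evaluable patients, meaning eligible and having received at least one dose, as section 3.1 defines them. Add that any inevaluable stage 1 patient is replaced, within the existing limit of 29 enrolments, before the rule is applied. Keep the requirement in section 7.3.3 that PFS6 is known for these patients.

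The cost is two wording changes. Typically 0 to 2 enrolments move from stage 2 to stage 1, and the enrolment limit does not change. The edit restores a 5.5% wrongful-stop probability, and 80.1% power provided 27 evaluable patients are reached. It does not address the cap: at 10% inevaluable, power remains about 77.3% with the gate corrected, and that needs its own decision.
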